3. TRIAL FLOW CHART

4. TRIAL SUMMARY

Title	The influence of anaesthetic depth on patient outcome after major surgery (The BALANCED anaesthesia study)
Project Office	Department of Anaesthesia and Peri-operative Medicine, Auckland City Hospital, [name]. [contact] [name], [contact], [contact]
Study Size	6,500 patients
Study Design	International multicentre double blind, prospective, intention to treat, safety and efficacy study
Primary Outcome	One year all-cause mortality
Secondary Outcomes	MI, cardiac arrest, pulmonary embolism, stroke, sepsis, surgical site infection, ICU stay, hospital stay, awareness, WHODAS score, persistent postoperative pain and cancer recurrence
Inclusion Criteria	≥60 years, ASA physical status 3 or 4, surgery lasting ≥2 hours, post-op hospital stay ≥2 nights, general anaesthesia with or without major regional block, able to monitor BIS
Study Protocol	
Pre-operative	Age, sex, weight, height, ASA physical status, ECG, haemoglobin, creatinine, albumin, Charlson co-morbidity score, WHODAS 12 item score
Intra-operative	Pre-defined mean arterial blood pressure target Randomised BIS target of 35 or 50 Computerised recording of BIS, SR, BP, HR, ETvol conc. Manual record of drugs administered and recovery indicators
Post-operative day 1-3	QoR-15 score, Analgesic and antiemetic requirements MI, cardiac arrest, pulmonary embolism, stroke, sepsis, surgical site infection, awareness (once)
Hospital Discharge	Length of hospital stay, unanticipated ICU admission, ICU stay, unplanned second operation
Post-operative day 30	Survival and disability free survival MI, cardiac arrest, pulmonary embolism, stroke, sepsis, surgical site infection, awareness, QoR-15 score, WHODAS 12 item score, persistent postoperative pain, staging of cancer
1 year follow-up	Survival and disability free survival MI, cardiac arrest, pulmonary embolism, stroke, sepsis, surgical site infection, WHODAS 12 item score, persistent postoperative pain, cancer recurrence

7. ABBREVIATIONS

ANZCA	Australian and New Zealand College of Anaesthetists
ASA	American Society of Anesthesiologists
BIS	Bispectral index
CRF	Case report form
DMC	Data monitoring committee
DVT	Deep vein thrombosis
ECG	Electrocardiogram
EEG	Electroencephalogram
GA	General anaesthesia
GCRP	Good clinical research practice
ICU	Intensive care unit
MAC	Minimum alveolar concentration (of a volatile anaesthetic)
MAP	Mean arterial pressure
mBPI	Modified brief pain inventory
MI	Myocardial infarction
MIBI	Technetium-99m with the ligand methoxyisobutylisonitrile scan
PE	Pulmonary embolus
QoR-15	Quality of recovery -15 item questionnaire
RCT	Randomised controlled trial
SD	Standard deviation
SR	Suppression Ratio (of EEG)
WHODAS	World Health Organisation disability assessment schedule 2.0, 12 item.

8. AIM OF TRIAL

Recent observational studies have found an association between deep anaesthesia and increased post-operative mortality in elderly and infirm patients undergoing major surgery. It is unknown whether there is a causal relationship in this observation, which occurs at levels of anaesthetic depth that are within the normal range of practice. We are performing a large randomised trial of 'deep' versus 'light' anaesthesia to definitively answer the question of whether anaesthetic depth alters perioperative outcome. Elderly patients undergoing major surgery will be randomised to an anaesthetic targeting either BIS=35 or BIS=50 for the deep and light groups respectively. The primary outcome variable will be all-cause mortality at one year and secondary outcomes will be MI, cardiac arrest, PE, stroke, sepsis, surgical site infection, ICU stay, hospital stay, awareness, WHODAS score, persistent postoperative pain and cancer recurrence.

Primary hypothesis

Light general anaesthesia (BIS = 50) is associated with decreased all cause mortality compared with deep general anaesthesia (BIS = 35) one year after major surgery in elderly patients.

Secondary hypotheses

Light general anaesthesia (BIS = 50) is associated with decreased incidences of MI, cardiac arrest, PE, stroke, sepsis and surgical site infection compared with deep general anaesthesia (BIS = 35) at 30 days and one year after major surgery in elderly patients.

Light general anaesthesia (BIS = 50) is associated with decreased incidences of a composite endpoint of MI, cardiac arrest, PE and stroke compared with deep general anaesthesia (BIS = 35) at 30 days and one year after major surgery in elderly patients.

Light general anaesthesia (BIS = 50) is associated with decreased cancer recurrence compared with deep general anaesthesia (BIS = 35) one year after major surgery in elderly patients.

Light general anaesthesia (BIS=50) is associated with an increased incidence of persistent postoperative pain compared with deep anaesthesia (BIS=35) at 30 days and one year after surgery in elderly patients.

Light anaesthesia (BIS = 50) is associated with increased disability-free survival compared with deep general anaesthesia (BIS = 35) one year after major surgery in elderly patients.

Safety and quality hypotheses

Light general anaesthesia (BIS = 50) is associated with improved early quality of recovery compared with deep general anaesthesia (BIS = 35) after major surgery in elderly patients.

Light general anaesthesia (BIS = 50) does not increase the incidence of awareness compared with deep general anaesthesia (BIS = 35) after major surgery in elderly patients.

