9. BACKGROUND

Anaesthetic depth monitoring in current anaesthetic practice

General anaesthesia uses a combination of intravenous hypnotics, anaesthetic vapours and gases, analgesics and muscle relaxants to create the anaesthetised state. This is known as balanced anaesthesia, a term first used by Lundy in 1926 [1]. It provides unconsciousness for patients, lack of movement to facilitate surgery and suppression of sympathetic reflexes sufficient to maintain reasonable body homeostasis. Current practice centres on ensuring adequate anaesthetic dosage to prevent awareness and movement, and titration of additional anaesthetic to prevent excessive sympathetic reflexes. Light anaesthesia speeds early recovery, decreases early post-operative nausea and vomiting and may reduce intra-operative hypotension [2-3]. However light anaesthesia also increases the risk of awareness, increases central sympathetic responses to the noxious stimulus of surgery, increasing bleeding, stress hormone release and inflammatory response and may increase post-operative pain [4-7]. For the past ten years, the technology to continuously monitor anaesthetic depth in individual patients using the EEG has been available. These devices, such as the bispectral index (BIS) monitor (Covidien, Dublin, Ireland) enable titration of anaesthetic depth to individual needs, rather than using population based dosing guidelines that ensure unconsciousness in almost everyone [8]. However, the optimal depth at which anaesthesia should be maintained is unknown, and indeed anaesthetic depth has not been the subject of patient outcome research, largely because until recently it could not be measured [9].

The BIS monitor measures the frontal lobe EEG using electrodes applied to the forehead. It presents the anaesthetic depth of the patient as an ordinal number between 98 (wide awake) and 0 (EEG electrically silent). The index represents mainly depression of the spectral edge frequency and power of the EEG between 100 and ~35 and the increasing level of burst suppression between ~35 and 0. Recommendations for routine general anaesthesia are to target values between 40 and 60. However there have been case reports of awareness at the upper end of this range, and patients are more commonly anaesthetised at levels of 30 - 50 [10]. When anaesthesia has been conducted with the BIS value hidden from the anaesthetist, this lower range has typically been where most anaesthetics were administered [10,11].

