13. SAMPLE SIZE AND STATISTICAL ANALYSIS

Primary outcome

One year all-cause mortality will be compared between randomised groups using a Mantel-Haenszel Chi-square test, stratified by study centre. A two-tailed p-value <0.049 will be taken to indicate statistical significance.

Power analysis

One year all-cause mortality is expected to be ~10% based on the findings of Leslie et al's study and Australasian studies [9,25]. The reduction in mortality in the light anaesthesia group is expected to be 20%. A power analysis using p1=0.10 and p2=0.08 indicates that N=3250 patients are required in each group, β =0.8, α =0.049. The alpha level is reduced to allow for the single interim analysis.

The primary and secondary outcomes will initially be analysed using the full analysis set population i.e. using those individuals who have confirmed outcomes. Sensitivity analyses will also be undertaken, as appropriate, for which those missing outcome data will be assigned a poor outcome. Complete listings, according to randomised group, will be compiled of those lost to follow-up, and include relevant explanations.

Secondary outcomes

The presence of MI, cardiac arrest, stroke, PE, sepsis, surgical site infection, awareness and persistent post-operative pain at 30 days and one year as appropriate will be compared between randomised groups using Mantel-Haenszel chi-square tests or Fisher's exact test depending on the expected cell frequencies. Additionally a composite score including the presence of any of MI, cardiac arrest, stroke and PE, will be compared between randomised groups also using a chi-square test.

Additional analyses will also explore the role of MI, cardiac arrest, stroke, PE, sepsis, surgical site infection and cancer recurrence on one year mortality using Cox's proportional hazards regression to develop a model of independent predictors of one year mortality. The randomised group will be added to this model to assist explanation of any observed differences in outcome between the randomised groups.

Secondary analyses will be undertaken on an intention to treat basis. The vast majority of participants will have assessments of the primary outcome (one-year mortality) and the 30-day secondary outcomes. Permission will be sought as necessary to extract these from national databases and local hospital records.

Adverse events

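### The protocol hypothesises no increase in awareness but gives it only a difference test, so a non-significant result cannot establish the safety claim

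*Protocol*

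**What the plan says.** Protocol section 8, under the safety and quality hypotheses, states that light anaesthesia (BIS 50) "does not increase the incidence of awareness compared with deep general anaesthesia (BIS = 35) after major surgery in elderly patients". It is the only hypothesis in that section that predicts no increase. The others predict a decrease, an increase or an improvement.

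Protocol section 13 (secondary outcomes) lists awareness with MI, cardiac arrest, stroke, PE, sepsis, surgical site infection and persistent pain. All of these "will be compared between randomised groups using Mantel-Haenszel chi-square tests or Fisher's exact test depending on the expected cell frequencies". The section states no margin, confidence-interval criterion, expected rate or power for awareness. Its only power calculation is for one-year mortality.

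On background risk, section 9 says in general terms that "light anaesthesia also increases the risk of awareness". It gives no incidence. The nearest it comes to suggesting that awareness is rare is a reference to "population based dosing guidelines that ensure unconsciousness in almost everyone".

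**The concern.** A claim of no increase is a non-inferiority claim. To support it, the data must exclude an increase large enough to matter. Chi-square and Fisher tests can show that the arms differ, but they cannot show that an increase of a given size is absent. With only these tests named, the stated hypothesis could be supported only by failing to reject equality, and a trial with few events fails to reject easily.

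This is more than detail left to an analysis plan. The protocol itself fixes both the hypothesis and the test, and the two do not fit together. At stake is a named safety conclusion about the light arm. The primary mortality result is not affected.

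**Working it through.** **1. The plan's own figure.** Section 13 gives 3250 per arm for 10% v 8% mortality at two-sided alpha 0.049, with the 0.8 read as power. The usual two-proportion formula is

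n = [z(α/2)·√(2p̄q̄) + z(β)·√(p₁q₁ + p₂q₂)]² / (p₁ − p₂)²

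With p̄ = 0.09 this is (1.9685 × 0.4047 + 0.8416 × 0.4045)² / 0.02² = 3233 per arm. Power at 3250 per arm is 80.2%. The stated size is reproduced, but it was set for mortality and says nothing about awareness.

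**2. Inputs for awareness.**
- 3250 per arm (section 13).
- Two-sided 5% level. This is assumed, because no level is stated for secondary outcomes.
- Deep-arm risk from 0.05% to 1%. This is assumed, because the protocol gives none.
- True light-arm risk set at twice the deep-arm risk.
- Centre strata ignored.
- Test chosen by expected count, as section 13 requires: Fisher when the pooled expected count is below 5 per arm, otherwise chi-square. The threshold of 5 is a convention and an assumption, because the protocol names none.

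**3. Power of the planned test to detect a doubling.** Power is the sum, over all pairs of event counts (i, j), of Bin(i; 3250, p) × Bin(j; 3250, 2p) wherever the test gives P < 0.05.

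| Deep-arm risk | Expected events, deep v light | Power, test chosen by expected count | Power, Fisher throughout | Doubling missed, test chosen by expected count |
|---|---|---|---|---|
| 0.05% | 1.6 v 3.3 | 3% | 3% | 97% |
| 0.1% | 3.3 v 6.5 | 13% | 10% | 87% |
| 0.2% | 6.5 v 13 | 32% | 24% | 68% |
| 0.5% | 16.3 v 32.5 | 65% | 60% | 35% |
| 1% | 32.5 v 65 | 92% | 90% | 8% |

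**4. Example results.**
- 3 v 6 events, with Fisher: P = 0.51. The exact 95% interval for the rate ratio is 0.43 to 12.4.
- 6 v 13 events, where the pooled expected count is 9.5 so chi-square applies: the difference is 7/3250 = 0.215 percentage points and the standard error is √(2 × 0.002923 × 0.997077 / 3250) = 0.134 points. So z = 1.61 and P = 0.11. The exact ratio interval is 0.77 to 7.0.

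Neither result is significant, and neither excludes a large relative increase.

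**5. What a non-inferiority reading could deliver.** Suppose the true risks are equal at p, the one-sided level is 0.025 and the margin is Δ. By normal approximation, which is rough at the smallest counts,

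power = Φ(Δ / √(2p(1 − p)/3250) − 1.96)

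Taking Δ = p, so that a doubling is excluded (for illustration only; the protocol sets no margin):

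| Deep-arm risk | Power to exclude a doubling at 3250 per arm | Per arm needed for 80% |
|---|---|---|
| 0.05% | 15% | 31,380 |
| 0.1% | 25% | 15,683 |
| 0.2% | 44% | 7,834 |
| 0.5% | 82% | 3,124 |
| 1% | 98% | 1,555 |

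The absolute margin that can be excluded with 80% power at 3250 per arm is (1.96 + 0.8416) × √(2p(1 − p)/3250). This is about 0.22 percentage points at 0.1%, 0.31 at 0.2% and 0.49 at 0.5%.

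**The case against.** The strongest reply is that the protocol nowhere says a non-significant result will be called proof of safety. Section 13 says only that the groups will be compared. It sets no rule for declaring the hypothesis supported and does not rule out reporting an interval. That is correct. A reader might infer such a rule, but the text supports only the narrower statement that the named test cannot establish the named hypothesis.

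Four other strong readings are tempting and are not supported.

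- **That the plan would back the safety claim almost whatever the truth, on very few events.** No awareness rate is given, and at 1% the planned test would detect a doubling about nine times in ten.
- **That a doubling would be missed 76–90% of the time at 0.1–0.2%.** This follows only if Fisher's test is used throughout. Section 13 chooses the test by expected counts, which gives about 68–87%.
- **That the protocol concedes harm in its own light arm.** The section 9 sentence is about light anaesthesia in general, not BIS 50 against BIS 35. The same section places case reports of awareness near the top of the 40–60 range, of which 50 is the midpoint. Section 12(d) describes the depths in current use as lying below the awareness level.
- **That awareness is the main hazard of light anaesthesia.** Section 9 lists it with bleeding, stress response, inflammation and pain, and does not rank them.

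It is also fair to say that awareness is one of thirteen secondary endpoints, that the data monitoring committee reviews safety every six months (section 18), and that an analysis plan not at hand could add a margin. These points limit the importance of the gap. They do not close it, because the protocol's own hypothesis and test would still not match. Nor is the trial uninformative on awareness: an interval for the absolute difference could be fairly narrow. That is a reason to base the conclusion on the interval.

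**Conclusion.** The point holds as a mismatch between the hypothesis in section 8 and the test in section 13. A non-significant chi-square or Fisher result would not establish that light anaesthesia does not increase awareness. This logical gap exists at any event rate.

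Its practical size is conditional. If the deep-arm risk is about 0.2% or lower, a true doubling would be missed roughly two times in three or more often. At 0.5% it would be missed about one time in three, and at 1% about one time in twelve. These figures rest on the assumed risks, a two-sided 5% level, unstratified tests and a threshold of 5 for the expected count. The text and the provision for Fisher's test are compatible with a rare event, but neither supplies a rate.

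This should be corrected because a named safety hypothesis depends on it. The sample size and the primary analysis do not.

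**What to change.** - In section 13, report the light-minus-deep risk difference in awareness with a score or exact 95% confidence interval. Judge the no-increase hypothesis only on the upper limit, against an absolute margin fixed and justified before unblinding.
- If no margin can be agreed, reword the hypothesis in section 8 as estimating the difference in awareness, and make no claim of no increase from a non-significant test.
- State the awareness rate assumed, so that readers can see what 3250 per arm can exclude. If that rate is 0.2% or lower, power to exclude a doubling is at most about 44%. An absolute margin or the estimation wording is then the realistic choice.

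The cost is wording in two sections and one interval calculation, with no extra patients or data. The downside is that the trial may have to report the awareness question as unresolved.

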9. BACKGROUND

Anaesthetic depth monitoring in current anaesthetic practice

General anaesthesia uses a combination of intravenous hypnotics, anaesthetic vapours and gases, analgesics and muscle relaxants to create the anaesthetised state. This is known as balanced anaesthesia, a term first used by Lundy in 1926 [1]. It provides unconsciousness for patients, lack of movement to facilitate surgery and suppression of sympathetic reflexes sufficient to maintain reasonable body homeostasis. Current practice centres on ensuring adequate anaesthetic dosage to prevent awareness and movement, and titration of additional anaesthetic to prevent excessive sympathetic reflexes. Light anaesthesia speeds early recovery, decreases early post-operative nausea and vomiting and may reduce intra-operative hypotension [2-3]. However light anaesthesia also increases the risk of awareness, increases central sympathetic responses to the noxious stimulus of surgery, increasing bleeding, stress hormone release and inflammatory response and may increase post-operative pain [4-7]. For the past ten years, the technology to continuously monitor anaesthetic depth in individual patients using the EEG has been available. These devices, such as the bispectral index (BIS) monitor (Covidien, Dublin, Ireland) enable titration of anaesthetic depth to individual needs, rather than using population based dosing guidelines that ensure unconsciousness in almost everyone [8]. However, the optimal depth at which anaesthesia should be maintained is unknown, and indeed anaesthetic depth has not been the subject of patient outcome research, largely because until recently it could not be measured [9].

The BIS monitor measures the frontal lobe EEG using electrodes applied to the forehead. It presents the anaesthetic depth of the patient as an ordinal number between 98 (wide awake) and 0 (EEG electrically silent). The index represents mainly depression of the spectral edge frequency and power of the EEG between 100 and ~35 and the increasing level of burst suppression between ~35 and 0. Recommendations for routine general anaesthesia are to target values between 40 and 60. However there have been case reports of awareness at the upper end of this range, and patients are more commonly anaesthetised at levels of 30 - 50 [10]. When anaesthesia has been conducted with the BIS value hidden from the anaesthetist, this lower range has typically been where most anaesthetics were administered [10,11].

Studies of the role of anaesthetic depth on perioperative outcome

Recently seven observational studies of the relationship between anaesthetic depth and patient outcome have been published (Table 1) [12-18]. Six of these studies have shown an association between relatively deep anaesthesia and increased subsequent mortality. However, various definitions of 'deep' anaesthesia have been used, centred on the duration the BIS value was either <45 or <40. The first study, by Monk, was a prospective observational study of 1064 patients undergoing major non-cardiac surgery [12]. All patients had BIS monitoring in addition to standard monitoring. Overall mortality was 5.5%, mortality in those over 65 years was 10.3%; 50% of deaths were due to cancer, there was a 24% increase in the risk of death per hour of deep hypnotic time and also a small increase in mortality if systolic blood pressure was less than 80 mmHg. The study implied that the anaesthetic itself may influence mortality. The study has been criticized for industry influence and the medical illness score (Charlson) being arbitrarily treated as bivariate [19,20]. Six subsequent studies have

been published using available databases. Five of these have found similar increases in mortality. In Lindholm et al.'s study, deep hypnotic time was not a predictor when pre-existing malignancy was included in the model. If deep hypnotic time was >2 hours subsequent mortality was much higher. Searleman et al.'s study found that non-surviving patients received slightly less volatile anaesthetic than the survivors, implying that patients who died may have been sensitive to the anaesthetic drugs. Saager et al.'s study used a very large database with 24,000 patients, and found three independent predictors of increased one year mortality, which were minimum alveolar concentration (MAC) <0.4, mean arterial pressure (MAP) <80 mmHg and BIS<40. (MAC is a normalised measure of anaesthetic potency). The risk to those who received deep anaesthesia was again a 20% increase in one-year mortality. Patients with a low MAP during the procedure faired even worse, and the combination of all three factors was associated with a RR=1.6 for one year mortality. They also found that patients who had an instance of low MAP, which was treated within 5 minutes had improved outcomes, indicating that although patients who were sensitive to anesthesia did poorly, early intervention was effective. Leslie et al analysed long-term outcomes in the B-Aware Trial, a 2,500 patient trial conducted principally in New Zealand, Australia and Hong Kong. This study also found an increased risk of myocardial infarction and cerebrovascular accident in the deep anaesthesia group. There were a large number of cardiac patients in the study and the same relationship of depth with poor outcome was confirmed, a finding repeated by Kertai et al. [17].

Author	Ν	ASA	1 y	Increased risk of
		3&4 *	mortality	death if 'deep' [#]
Monk 2005 [12]	1064	35%	5.5	RR = 1.24
Lindholm 2009 [13]	4087	6%	4.3	HR = 1.18
Saager 2009 [14]	23,999	~30%	4.8	RR = 1.63
Searleman 2010 [15]	1791	71%	10.7	OR = 1.25/h
Leslie 2010 [16]	2463	74%	10.8	PS = 1.42 (at 4y)
Kertai 2010 (cardiac) [17]	460	100%	17.8	HR = 1.29 (at 3y)
Kertai 2011 (non-cardiac) [18]	1473	60%	24.3	HR = 1.03 (at 3y)

TABLE 1 Observational studies of the relationship between depth of anaesthesia and subsequent mortality

*ASA=American Society of Anaesthesiologists physical status scale, 1=normal health, 2=mild to moderate systemic disturbance, 3=severe systemic disturbance which limits activity, 4=incapacitating life threatening disease, 5=moribund.

[#]RR=relative risk, HR=hazard ratio, OR=odds ratio, PS=propensity score

These studies imply a greater role for anaesthesia in determining surgical outcome than previously suspected, but have been greeted with disbelief by the anaesthetic fraternity, rather than the design of robust studies investigating causality [19-21]. The question of the best depth at which to give general anaesthesia has not been addressed in large randomised trials. The marketing and use of processed EEG monitors such as BIS has been largely based on their use to prevent awareness under anaesthesia. All six study groups have recommended that prospective randomised studies are required to determine whether causality exists in the excess mortality rate, as have three accompanying editorials [10,19,21], however none of the investigators has commenced such a study (personal communications). The fact that multiple observational studies have been positive reduces the risk that the phenomenon is a simple case of publication bias [22].

An audit of 6,984 BIS monitored anaesthetics performed at Auckland City Hospital found the median BIS to be 38 (SD 8) [23]. Over 50% of patients had a BIS <40 for >1 hour. This is in line with the typical anaesthetic depths found in the studies mentioned above, but indicates our current work practices may put patients at similar risk. Past studies from Australia and New Zealand have shown that the elderly and the sick, defined as aged over 70 years and ASA physical status 3 or 4, have an expected mortality at one year of ~10% and are therefore most at risk of mortality as a result of sensitivity to anaesthesia [24].

Possible advantageous and deleterious effects of overly deep anaesthesia

There have been two small clinical studies looking at the influence of anaesthetic depth on postoperative pain. A study on 71 morbidly obese patients undergoing gastric banding found a decrease in visual analogue scores (VAS) for pain and decreased morphine requirements in patients who had consistently deep anaesthesia, as assessed by a spectral edge frequency target of 8-12 Hz [25]. These patients had average end tidal isoflurane concentrations of 0.81% vs 0.7% in the light group. Hennenberg et al. found a similar result in 43 patients undergoing gynaecological procedures using propofol and remifentanil, and guided by middle latency auditory evoked potentials [26]. It was, however, possible that the results were due to increased residual sedation in the 'deep' anaesthesia group. Indeed a randomised prospective study of 20 patients undergoing elective hysterectomy reported no difference in VAS-pain or morphine consumption and also no difference in plasma cortisol, glucose or lactate concentrations [27]. This study used desflurane anaesthesia with a target BIS of 50 or 25. Desflurane concentrations were 4% and 9% in the light and deep groups respectively.

The possible deleterious effects of anaesthesia are protean [28-34]. In animal models, anaesthesia can provoke the inflammatory response, increase deposition of Alzheimer's proteins, induce neuronal apoptosis and cause prolonged post-anaesthetic cognitive dysfunction. Neuronal apoptosis in particular is also induced by burst suppression of the EEG. These effects occur with both volatile anaesthetic agents such as isoflurane and intravenous agents such as propofol. Opioids also induce tissue angiogenesis by a peripheral effect and may decrease cancer survival times [35]. Other pharmacological effects of anaesthetic agents include immune depression and direct tissue toxicity. There may also be indirect physiological effects due to cardiovascular or neuronal depression causing tissue hypoperfusion and hypoxia [21,36,37].

The relationship between deep sedation and adverse outcomes including mortality has also been demonstrated in intensive care medicine [37,38]. Burst suppression is a common consequence of surgical anaesthesia that is unlikely to occur at the higher BIS targets which equate to light anaesthesia [39].

If any of these possible causes are confirmed to be increasing mortality, then a study such as the one that we propose, looking at outcome at two different levels of anaesthetic depth becomes a question of dose-response effects and whether a lower dose of anaesthetic is safer.

Could organ hypoperfusion be the problem?

We recently proposed a model to explain the complex interplay among the various perioperative factors that may lead to a poor outcome – relative anaesthetic overdose, organ dysfunction and organ hypoperfusion (each of which may lead to a low BIS value and result in an apparent association between low BIS values and death) (Figure 1) [9]. We observed that the apparent association between low BIS values (low MAC and low MAP) and death is likely to be due to anaesthetic intolerance (a marker of illness?) rather than inherent anaesthetic toxicity. The tantalising question is whether preventing relative anaesthetic overdose and/or low BIS values, whilst maintaining adequate organ perfusion, will make any difference. The simple answer to this complex question is a well-controlled randomised trial of a large group of patients at high risk of postoperative morbidity and mortality, such as the one we propose.

[figure not shown]

Figure 1. Model of low processed electroencephalographic (EEG) index values and their relationship to perioperative morbidity and mortality. Organ dysfunction = organ disease, genetic malfunction, or toxicity.

Recent Literature

The Saager study which was published as conference proceedings has now been published using one-month mortality as the primary outcome variable by Sessler et al., with an accompanying editorial [40,41]. The study included 24,170 adult patients, mean MAP, BIS and MAC were determined and patients divided into three groups for each variable –high, medium or low. The medium group served as a reference for relative risk of lengthened hospital stay and 30 day mortality in the other groups. Reference means were MAP=87 \pm 5 mmHg, BIS = 46 \pm 4 and MAC = 0.56 \pm 0.11. 30-day mortality was doubled in double low combinations and quadrupled in the triple low group (Table 2). Unfortunately demographic data for each of these groups are not available so it is difficult to directly compare this study with the earlier ones. It is of note that a recent abstract from another large tertiary hospital has found a similar association in a retrospective study of 20,146 patients [42]. This finding strengthens the possibility that organ hypoperfusion may be part of the problem, and that this is detected by the BIS as a low reading.

A recent prospective study of 73 patients has found decreased cerebral oxygenation using non-invasive cerebral oximetry (SICO-Somanetics Invos Cerebral Oximeter, Covidien Inc, Co, USA) in patients with low BIS and subsequent post-operative cognitive dysfunction persisting out to 52 weeks, indicating hypoperfusion of the brain may be part of the problem, that is reflected by overly deep anaesthesia and anaesthetic sensitivity [43]. The same study also found an association with raised S100B plasma concentrations in those that had prolonged anaesthesia, or anaesthesia outside of the target range. The S100B protein is a marker of brain injury.

TABLE 2 Adapted from Sessler 2012 [40]. Relationship between blood pressure, anaesthetic depth, volatile anaesthetic use and 30-day mortality in 24,000 patients. The paired combinations of lows were all associated with worse outcome.

MAP/BIS/MAC state	Ν	MAP	BIS	MAC	30 day Mortality	Hazard Ratio	Р
REF (med/med/med)	8034	87	46	0.56	0.5	1.0	<0.001
High/high/low	1653	96	56	0.38	1.1	1.11	0.19
Low/high/high	2070	78	54	0.72	0.4	0.97	0.63
High/low/high	2985	97	39	0.72	0.2	0.95	0.37
Low/high/low	2332	77	56	0.38	1.6	1.14	0.05
High/low/low	1782	97	38	0.39	1.0	1.21	0.01
Low/low/high	1798	79	39	0.72	1.0	1.08	0.28
High/high/high	1971	96	53	0.73	0.5	0.90	0.13
Low/low/low	1459	78	38	0.37	2.9	1.47	<0.001

[figure not shown]

Figure 2

30-day mortality in patients who had a mean MAC=0.6 during their anaesthetic (the low group). The figure demonstrates the marked effect of either low BIS or low MAP and mortality [40].

A much larger study of postoperative delirium and cognitive decline in 921 patients aged over 60 years and undergoing major non-cardiac surgery has compared BIS guidance between 40 and 60 with standard of care and BIS concealment [44]. Patients in the control group had lower BIS values (mean 36) compared to the treatment group (mean 53). There was a 30% reduction in volatile anaesthetic use, significantly less delirium in the BIS guided group (16% vs 24% incidence) and significantly less postoperative cognitive dysfunction at three months (10% vs 15% incidence). Most patients were ASA physical status 1 and 2. The study was not powered to detect a difference in mortality, but interestingly found evidence of predominantly deep anaesthesia in the control group, when anaesthesia was not BIS guided.

A pilot study of the proposed trial methodology

A pilot study of 125 patients has been completed at six hospitals in New Zealand, Australia and Hong Kong [45]. The study was approved as meeting current ethical committee requirements in all three jurisdictions, and was also approved by the Māori research review committee at Auckland District Health Board. The study protocol was found to be acceptable to our patients and anaesthetists and no ethical concerns were raised. The results reassured us that BIS targets could be met, that a lower blood pressure in the 'deep' group was not a confounding factor and demonstrated a 50% higher anaesthetic dose in the deep group (Table 3). The pilot study also allowed us to refine details of the protocol and perform an accurate costing.

A summary of one-month and one year outcomes is presented in Table 4. It must be noted that although there are differences in the two groups in one of these outcomes, the study is under powered to attach any significance to this difference.

	BIS 35	BIS 50
Ν	61	64
Duration (min), mean (sd)	198 (79)	196 (105)
BIS (mean (sd) of means)	39 (5)	48 (6)
MAC (mean (sd) of means) *	0.95 (.23)	0.63 (.19)
MAP (mean (sd) of means) [#]	86 (11)	89 (10)

TABLE 3: Pilot study, depth, volatile anaesthetic dosing and mean arterial pressures

*MAC is minimum alveolar concentration of anaesthetic vapour. *MAP is mean arterial pressure

TABLE 4: One month and one year outcomes in the pilot study

Outcome		BIS 35	BIS 50
Primary			
Ν		61	62
Mortality		7 (11%)	6 (9%)
Secondary			
Time to dis	charge from recovery (min)	61	62
Discharge from hospital (days)		10.1	8.2
Surgical site infection		8 (13%)	2 (3%) [#]
Composite complications score*			
	At one month	19 (31%)	11 (17%)
	At one year	9 (15%)	3 (5%)
Cancer			
	Pre-op.		30 (48%)
	At one year	20 (33%)	13 (21%)

*Composite complications score = 'yes' to any of myocardial infarction, congestive cardiac failure, pulmonary embolus, deep vein thrombosis, pneumonia or stroke in first month after surgery *P=0.029 (Chi Square)

Rationale for Research

Over 234 million people worldwide undergo surgery each year for both acute and chronic conditions [46]. Most of these people receive general anaesthesia. Over 10% are having moderate or major operations and are in the higher risk categories that are the target study group. These are the patients most likely to benefit should the study show that light anaesthesia is preferable.

Current public perceptions are that anaesthesia is very safe and indeed in healthy patients mortality purely attributable to the anaesthesia used is ~1:200,000 anaesthetics. However the influence of anaesthetic technique on perioperative outcome has barely been explored. Where such trials have been performed, they have also not shown the expected results. The MASTER trial, conducted in Australia and New Zealand in the 1990's comparing major regional anaesthesia for post-operative pain relief with intravenous analgesics showed no difference in mortality in spite of strong evidence from meta-analysis [47,48]. The POISE trial, a major international trial with strong Australian and New Zealand input on the role of beta-blockade in preventing myocardial infarction and death in patients with ischaemic heart disease also showed increased mortality. This was due to an unexpected increase in strokes counterbalancing the expected decrease in myocardial infarctions [49]. These results have led to a call for more such outcome studies to be performed to answer important public health questions about how we conduct anaesthesia.

The ANZCA Trials Group

The ANZCA Trials Group arose from the informal group of interested anaesthetists and hospitals that have participated large scale outcome studies in Australasia.

These studies include:

Master	Multicentre Australian study of epidural anaesthesia [47]
B-Aware	Bispectral index monitoring to prevent awareness during general anaesthesia [50]
